#### *4.7.5 Definition of Serious Adverse Event (SAE)*

Any untoward and unexpected medical occurrence or effect that:

- Results in death
- Is life-threatening – refers to an event in which the subject was at risk of death at the time of the event; it does not refer to an event which hypothetically might have caused death if it were more severe
- Requires hospitalisation, or prolongation of existing inpatients' hospitalisation
- Results in persistent or significant disability or incapacity
- Is a congenital anomaly or birth defect

An SAE form will be completed and forwarded to the sponsor or delegated representative within 24 hours. However, relapse and death and hospitalisations for elective treatment of a pre-existing condition do not need reporting as SAEs. All SAEs should be reported to the study sponsor local Research Ethics Committee where in the opinion of the Chief Investigator, the event was:

- 'Related', i.e. resulted from the administration of any of the research procedures; and
- 'Unexpected', i.e. an event that is not listed in the protocol as an expected occurrence

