#### *4.7.6 Reporting Procedures for All SAEs*

Reports of related and unexpected SAEs should be submitted within 15 days of the Chief Investigator becoming aware of the event, using the 'COREC SAE' form for non-CTIMP studies. Local investigators should report any SAEs as required by their Local Research Ethics Committee and/or Research & Development Office. Fatal or life-threatening SAEs must be reported within 7 days which will be reported to the Competent Authorities MHRA and the Research Ethics Committee.

SAE reports must be sent to R&I using one of the following methods:

- i. Email: [contact]
- ii. Hand Delivered (Not Mailed): [name]
- iii. [contact] (If written report not immediately possible)

The intensity of the AE will initially be assessed according to the following definitions:

- *Mild*: An event easily tolerated by the participant, causing minimal discomfort, and not interfering with everyday activities
- *Moderate*: An event sufficiently discomforting to interfere with everyday activities
- *Severe*: An event that prevents everyday activities

All AE and SAE Reporting documentation (i.e. NHS National Patient Safety Agency, National Research Ethics Service, Report of Adverse Event (AE) and Serious Adverse Event) physical copies of these will be kept in the Trial Master File.

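### Section 4.7.5 makes a fatal event an SAE and then exempts death from SAE reporting, while Section 4.7.6 requires fatal SAEs to be reported within 7 days

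*Protocol*

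**What the plan says.** Protocol Section 4.7.5 defines an SAE as "Any untoward and unexpected medical occurrence or effect that" meets one of five criteria. The first is "Results in death". The list also includes life-threatening events and events meeting "Requires hospitalisation, or prolongation of existing" inpatient stay. The duty to report follows the list: "An SAE form will be completed and forwarded to the sponsor or delegated representative within 24 hours".

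The next sentence is the exemption: "However, relapse and death and hospitalisations for elective treatment of a pre-existing condition do not need reporting as SAEs". After it, Section 4.7.5 sends SAEs to the REC when the Chief Investigator considers them both related and unexpected.

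Section 4.7.6 adds two time limits:

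- For related and unexpected events: "Reports of related and unexpected SAEs should be submitted within 15 days of the Chief Investigator becoming aware of the event".
- For the gravest events: "Fatal or life-threatening SAEs must be reported within 7 days which will be reported to the Competent Authorities MHRA and the Research Ethics Committee".

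**The concern.** The same event is put into SAE reporting by one sentence and taken out by the next, and the following section assumes it is still in. The protocol gives no order of precedence.

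What is at stake is safety oversight. Participants perform maximal incremental cycle tests on two consecutive days, and Section 4.3 acknowledges that deaths have been reported with graded exercise testing. A death connected with a study test is the event for which expedited reporting most needs to be unambiguous. The 24-hour, 15-day and 7-day routes are all worded for SAEs. If a site reads the exemption as removing death from SAE reporting, none of them need be triggered.

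**Working it through.** This is a conflict of wording, so there is no figure of the plan's to reproduce. The check sets the rules side by side, tests whether any other text resolves them, and then traces what happens to a death.

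**The rules for a fatal event**

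| Place | Effect on a fatal event | Deadline | Recipient |
|---|---|---|---|
| 4.7.5, criteria | Is an SAE if untoward and unexpected | – | – |
| 4.7.5, form | Must be reported on an SAE form | 24 hours | Sponsor or delegate |
| 4.7.5, exemption | Need not be reported as an SAE | none | none |
| 4.7.6, fatal SAEs | Must be reported | 7 days | MHRA and REC |
| 4.7.6, related and unexpected SAEs | Should be reported | 15 days from the Chief Investigator's awareness | Not named in that sentence; 4.7.5 sends such events to the REC |

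Rows two and four cannot both be relied on alongside row three.

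**Readings that might remove the conflict**

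1. *The closing reference to a pre-existing condition also limits death.* The grammar ties it to elective hospitalisation. Even if it is extended, deaths from a pre-existing condition would be exempt, and neither the death criterion nor the 7-day rule makes that exception.
2. *The SAE definition covers only unexpected events, so expected deaths are outside it anyway.* The exemption is not confined to expected deaths. It also covers unexpected and procedure-related ones.
3. *A disease-related exemption was meant.* Section 4.7.1 leaves signs of the disease under study out of the AE definition unless they are more severe than expected. This may be what the author had in mind, but Section 4.7.1 does not mention death and Section 4.7.5 neither repeats that limit nor refers to it.
4. *Section 4.7.5's later sentence sending related and unexpected SAEs to the REC overrides the exemption.* It applies to SAEs, and the exemption can be read as removing death from SAE reporting first.
5. *Death is recorded elsewhere.* Section 4.1.2.6 gives death its own grade on the functional status scale. That is an outcome grade, not a safety report.

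None of these resolves the conflict.

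**What happens to a death if a site follows the exemption**

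- *A life-threatening event or unplanned hospitalisation came first.* Both remain separate SAE criteria. The life-threatening one "refers to an event in which the subject was at risk of death at the time of the event". A report may therefore already exist, and the gap is narrow.
- *No such report came first, for example a sudden death at home.* No SAE form is required under the exemption, so the 24-hour and 7-day routes may not start. This is the widest gap.
- *The death was also related and unexpected.* The 15-day route is in doubt too.

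**What still operates**

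- Section 4.7.4 asks for prompt notice of AEs and SAEs to a University of Derby office, and Section 7.0 names that university as sponsor. There is no fixed deadline, and neither the REC nor the MHRA is named.
- Section 4.7.4 also relies on local NHS Trust procedures. These give no deadline in the protocol and do not fit the sites in the USA and India.
- AEs are entered on the CRF, but Sections 5.0 and 6.2 keep paper CRFs until the study end date before central data entry.
- Section 5.0 provides for an independent monitor of study data, with no deadline for reporting a death.
- Section 4.7.6 leaves further reporting to local REC or R&D requirements, again worded for SAEs.

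**How often the clause might operate**

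Section 4.3 cites 0 to 1 death per 10,000 tests, mostly in cardiac patients. The synopsis plans 150 participants with two tests each, so 150 × 2 = 300 tests. The expected number of test-related deaths is 300 × 0/10,000 = 0 to 300 × 1/10,000 = 0.03. This assumes that the cited range applies to this population and leaves out deaths from other causes.

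**The case against.** The strongest reply is that the exemption is permissive and the 7-day rule is mandatory. The exemption does not forbid reporting or take death out of the SAE definition. A site that reports every death complies with both sections, and non-reporting arises only if a site prefers the permissive sentence. Other channels also remain: Trust procedures, the CRF, the data monitor, local REC or R&D rules, and notice to the sponsor's office. Follow-up is short, patients treated in intensive care are excluded, and at most 0.03 test-related deaths would be expected. On this view the point is a minor wording correction.

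Part of this stands. The sponsor would probably hear of a death, the event is rare, and nothing in the analysis depends on it. It does not remove the conflict. A site that reads the exemption literally is following the protocol as written, and the 7-day rule applies only to events treated as SAEs. None of the other channels sets a fixed deadline for reporting a death. Rarity limits how often the fault would matter, but not its consequence when it does.

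**Conclusion.** The concern holds. Section 4.7.5 contradicts its own first SAE criterion and conflicts with the 7-day rule in Section 4.7.6, and no other text in the protocol reconciles them. No numerical effect size applies. In terms of reporting, two fixed deadlines (24 hours to the sponsor; 7 days to the MHRA and REC) are in doubt for any fatal SAE, and the 15-day deadline is in doubt if the death was also related and unexpected. The only other timing instruction is the open-ended one to the sponsor's office.

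This rests on the exemption being read as written, without a limit on cause or relatedness. If the sponsor meant a narrower, disease-related exemption, the fault lies in leaving that limit unstated. Sample size, error rates and planned analyses are unaffected. It should be fixed because the event is improbable but grave and the correction is simple.

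**What to change.** Reconcile Section 4.7.5 with Section 4.7.6 in one of two ways:

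- take death out of the exemption sentence; or
- if a limited exemption was intended, state exactly which deaths it covers, worded so that no death related to a study procedure falls outside SAE reporting, and make the 7-day rule in Section 4.7.6 consistent with it.

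The choice is the sponsor's. The cost is one wording amendment under Section 6.1: the sponsor categorises it and it is reported to the REC. If it needs REC approval, it takes effect only after REC and R&I approval. No new procedure, form or analysis is needed.

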#### *4.7.6 Reporting Procedures for All SAEs*

Reports of related and unexpected SAEs should be submitted within 15 days of the Chief Investigator becoming aware of the event, using the 'COREC SAE' form for non-CTIMP studies. Local investigators should report any SAEs as required by their Local Research Ethics Committee and/or Research & Development Office. Fatal or life-threatening SAEs must be reported within 7 days which will be reported to the Competent Authorities MHRA and the Research Ethics Committee.

SAE reports must be sent to R&I using one of the following methods:

- i. Email: [contact]
- ii. Hand Delivered (Not Mailed): [name]
- iii. [contact] (If written report not immediately possible)

The intensity of the AE will initially be assessed according to the following definitions:

- *Mild*: An event easily tolerated by the participant, causing minimal discomfort, and not interfering with everyday activities
- *Moderate*: An event sufficiently discomforting to interfere with everyday activities
- *Severe*: An event that prevents everyday activities

All AE and SAE Reporting documentation (i.e. NHS National Patient Safety Agency, National Research Ethics Service, Report of Adverse Event (AE) and Serious Adverse Event) physical copies of these will be kept in the Trial Master File.

## **5.0 Data Protection and Patient Confidentiality**

All investigators and study site staff will comply with the requirements of the Data Protection Act 2018 with regards to the collection, storage, processing, and disclosure of personal information and will uphold the Act's core principles. This includes a trial independent monitor which will carry out the monitoring of the study data as an on-going activity.

Staff involved in the study will ensure that all participants' confidentiality is maintained. The participants will be identified only by initials and surname (for purposes of address on the telephone), and a unique patient study identification number on the CRF and central electronic database. All documents will be stored securely and only accessible by staff involved in the study and authorised personnel. The study will comply with the Data Protection Act (in the UK) and with local legal requirements alongside the principles of ICH-GCP (worldwide); in line with this, all data will be anonymised as soon as it is practical to do so. The fully anonymised study data will be stored for at least five years following the closure of the study and thereafter disposed of in line with regulatory requirements. No participant will be individually identified in any subsequent publications relating to this study.

The study database will be kept on Microsoft Excel© 2016 and hosted on the University of Derby internal server. The server and database are protected by several measures including anti-virus and anti-spyware applications, firewalls, encryption technology and permissions. Data will be entered onto the paper CRF and retained and stored securely until the study end date, at which point the CRFs will be sent securely to the coordinating centre for entry onto the electronic study database. The data will be securely stored in line with ICH-GCP standards and data protection principles. The data stored will be checked for missing or unusual values and for consistency within participants over time. If any problems are identified, the appropriate CRFs will be reviewed in discussion with relevant local site personnel and queried for confirmation or correction as required until resolution.

The Chief and Principal Investigators, sponsor, and authorised staff will have access to participants' data. The Chief Investigator and/or Principal Investigators will facilitate access to study records for monitoring, audits, and regulatory inspections.

## **6.0 Data Retention and Archiving**

In compliance with the ICH/GCP guidelines, regulations and following the University Hospitals NHS Trust Code of Research Conduct and Research Ethics the Chief Investigator will maintain all records and documents regarding the conduct of the study. These will be retained for at least 15 years (or for longer if required). If the Chief Investigator is no longer able to maintain the data records, an alternative person will be nominated to take over this responsibility.

The Trial Master File and Trial documents held by the Chief Investigator on behalf of the Sponsor shall be finally archived by the sponsor local NHS Trust. This archive shall include all study databases and associated meta-data encryption codes.

## 6.1 Amendments

Amendments to the study protocol will be handled according to the Health Research Authority's guidelines for Non-CTIMP studies. Decisions to amend the protocol will be the responsibility of the Sponsor in consultation with the Chief Investigator and Principal Investigator. The Sponsor will have responsibility for determining the category of each amendment (Substantial versus Non-Substantial). All substantial and non-substantial amendments will be reported directly to the local Hospitals Trust Research Ethics Committee. It will be authorised by the Sponsor and Chief Investigator before submission. The appropriate documentation, clearly detailing changes, will be emailed to the responsible REC for review. Should a protocol amendment be made that requires REC approval, the changes in the protocol will not be instituted until the amendment and revised participant consent forms and participant information sheets (if appropriate) have been reviewed and received approval from the REC and R&I departments. A protocol amendment intended to eliminate an apparent immediate hazard to participants may be implemented immediately providing that the MHRA, R&I and REC are notified as soon as possible, and approval is requested. Minor protocol amendments only for logistical or administrative changes may be implemented immediately and therefore the REC will be informed.

## 6.2 Access to the Final Study Dataset

The study database will be kept on Microsoft Excel© 2016 and hosted on the local University server. The server and database are protected by many measures including anti-virus and anti-spyware applications, firewalls, encryption technology and permissions. Data will be entered onto the paper CRF and retained and stored securely until the study end date, at which point the CRFs will be sent securely to the coordinating centre for entry onto the electronic study database.

The data will be securely stored in line with ICH-GCP standards and data protection principles. The data stored will be checked for missing or unusual values and for consistency within participants over time. If any problems are identified, the appropriate CRFs will be reviewed in discussion with relevant local site personnel and queried for confirmation or correction as required until resolution. The Chief and Principal Investigators and authorised staff will have access to participants' data. The Chief Investigator and/or Principal Investigators will facilitate access to study records for monitoring, audits, and regulatory inspections.

## 7.0 Financing and Insurance

This study is funded by GILEAD Sciences: COVID-19 RFP Program to the value of £174,885.46.

Indemnity and insurances will be provided by the University of Derby who is acting as the sponsor for this study.

## 7.1 Participant Incentives

There will be no financial recompense for the participants time, however all expenses (parking and travel) will also be covered by the study.

## 7.2 Funding

The study is funded by GILEAD Sciences: COVID-19 RFP Program

## 8.0 Public Patient Involvement

This protocol has been reviewed as part of the PPI groups at Royal Derby Hospital, UK and Patient involvement in Research Group (PIRG) at the Advanced Wellbeing Research Centre, UK.

## 9.0 End of Study

The end of the study is the date of the home visit (post-study follow up) of the last participant enrolled.

## 10.0 Discontinuation/Withdrawal of Participants from Study Treatment

Each participant has the right to withdraw from the study at any time. Participants may be withdrawn from the study either at their request or at the discretion of the Chief Investigator. Participants will be made aware (via The Participant Information Sheet and Participant Consent Form) that withdrawing the data which has been collected cannot be erased and may still be used in the final data analysis and study dissemination (i.e. published journal). The Chief Investigator may withdraw a participant from the study at any time if they consider that the participant's health is compromised by remaining in the study or the participant is not sufficiently cooperative. The reasons for any participant withdrawal will be recorded on the study completion form of the CRF. The data collected from withdrawn participants will be included in the study report.

Besides, the Chief Investigator may discontinue a participant from the study at any time if they consider it necessary for any reason including but not limited to:

- Ineligibility (arising during study or retrospective having been overlooked at screening)
- Significant protocol deviation
- Significant non-compliance with study requirements
- An AE which results in the inability to continue to comply with study procedures
- Progression of illness that renders participants unable to comply with study procedures.
- Consent is withdrawn
- Lost to follow up

The reason for withdrawal will be clearly stated and recorded in the CRF.

If the participant is withdrawn due to an AE, the Chief Investigator will arrange for a follow-up telephone call until the AE has resolved or stabilised.

## 11.0 Dissemination

All data arising from this study will be owned by the named academics from the University of Derby. On completion of the study, the data will be analysed and reported into a final study report. The full study report will be accessible via the Chief Investigator.

There shall be no publication or dissemination of the conclusions of the study, including all or any part of the results of the study, without the prior written consent of the Chief Investigator and the Sponsor, such consent not to be unreasonably withheld or delayed. There shall be no publication or other dissemination of the conclusions of the study until the Sponsor has approved the conclusions of the study.

There are no plans to notify the participants of the outcome of the study. Participants may specifically request results from the PI; this information would be provided after study results have been published. The study protocol, full study report, anonymised participant-level dataset, and statistical code for generating the results will not be made publicly available.

Manuscripts resulting from the research will be conceived, written, and published at the discretion of the Chief Investigator, in conjunction with the Principal Investigator and other members of the research team as appropriate. This activity will be independent of the Research Funder, who will not have any control over the content or results of any publications. It is anticipated that the research will lead to publications in subject-specific international peer-reviewed journals and presentations at international conferences.

### 11.1 Authorship eligibility guidelines and any intended use of professional writers

Authorship will be determined by the research team on the final study report and subsequent publications, following the International Committee of Medical Journal Editors guidance for authorship of manuscripts submitted for publication. Professional writers will not be employed.

